6 STATISTICAL AND ANALYTICAL PLANS

The planned tables and listings are presented in Section 7.

6.1 Changes in the Planned Analyses

There has been no changes to the planned analyses.

6.2 Blind Review

Details regarding a blind review of data will be specified in the Pre-Analysis Review Form.

6.3 Hypotheses and Statistical Methods

6.3.1 Definitions

Baseline Visit 1 is defined as the baseline visit, however if a measurement is retaken at Visit 2 before dosing this will be used as the baseline value instead of the Visit 1 value. This concerns laboratory measurements, vital signs, physical examination and concomitant medication (including insuline use). For fasting glucose baseline is defined as the average of the -10 minute and 0 minute values at screening (Visit 1).

Difference from baseline

The difference from baseline is defined as the difference from the baseline according to the definition above.

Relative day The relative day of an event is derived as:

$$\text{Relative day} = (\text{Start date}) - (\text{Date of first administration of IMP}) + 1$$

For events occurring or starting before the date of first administration of IMP, the relative day is derived as:

$$\text{Relative day} = (\text{Start date}) - (\text{Date of first administration of IMP})$$

In this way, there will be no Day 0. Day 1 is the same day as the day of first administration of IMP, and Day -1 is the day before.

TEAE A TEAE is defined as any adverse event (AE) not present prior to the initiation of the treatment(s) or any AE already present that worsens in either intensity or frequency following exposure to the treatment(s).

6.3.2 Summary Statistics

Descriptive statistical methods will be used to summarize the data from this study. Unless stated otherwise, the term descriptive statistics refers to number of patients (n), mean, median, standard deviation (SD), standard error of the mean (SEM), minimum and maximum for continuous data and counts and percentages for categorical data.

Summary statistics will be presented per cohort (based on age group and number of capsules), treatment group and assessment time and/or visit, as applicable. The groups will be divided into single dose for 2 and 6 capsules, repeat dose for 2 and 6 capsules, Active and Placebo. See Table 1 for details.

Table 1

Cohort	Treatment	Number of AG019 capsules per day	Total Number of teplizumab infusions	Age Group
AG019 Cohort 1	AG019, single dose	2	NA	Adults
AG019 Cohort 1	AG019, repeat dose	2	NA	Adults
AG019 Cohort 2	AG019, single dose	6	NA	Adults
AG019 Cohort 2	AG019, repeat dose	6	NA	Adults
AG019 Cohort 3	AG019, single dose	2	NA	Adolescents
AG019 Cohort 3	AG019, repeat dose	2	NA	Adolescents
AG019 Cohort 4	AG019, single dose	6	NA	Adolescents
AG019 Cohort 4	AG019, repeat dose	6	NA	Adolescents
Combination Cohort 1	AG019, repeat dose + teplizumab infusion	6	12	Adults
Combination Cohort 1	Placebo capsules, repeat dose + Placebo infusion	6	12	Adults
Combination Cohort 2	AG019, repeat dose + teplizumab infusion	6	12	Adolescents
Combination Cohort 2	Placebo capsules, repeat dose + Placebo infusion	6	12	Adolescents

NA: not applicable

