10.7. Safety Analysis

Safety will be assessed based on TEAEs, physical examination findings, vital sign measurements and clinical laboratory tests.

Adverse events will be coded to a Medical Dictionary for Regulatory Activities (MedDRA) preferred term and system organ classification. The occurrence of treatment emergent AEs will be summarized by treatment frequency received using preferred terms, system organ classifications and severity. If a patient experiences multiple events that map to a single preferred term, the greatest severity and/or strongest investigator assessment of relation to study drug will be assigned to the preferred term for the appropriate summaries. Separate summaries of treatment emergent SAEs and treatment emergent AEs that are related to either IMP will be generated. Summaries may be repeated according to study phase. All AEs will be listed for individual patients showing both verbatim and preferred terms.

Descriptive summaries of vital signs and quantitative clinical laboratory changes will be presented by treatment received and study visit. The number and percentage of patients experiencing laboratory abnormalities and clinically relevant laboratory abnormalities will be summarized by treatment received. Cross tabulations of baseline abnormality vs. worst post treatment abnormality for selected laboratory assessments will presented by treatment received.

Abnormal physical examination findings will be presented by treatment received. The number and percentage of patients experiencing each abnormal physical examination finding will be included.

Prior and concomitant medications will be coded using the World Health Organization (WHO) dictionary. These data will be listed.

The number and percentage of patients with presence of sAGX0407 bacteria will be summarized by treatment group.

10.8.Interim Analysis

Interim analyses will be performed according to the below schedule:

After the last Day 180 follow-up visit of the last patient enrolled into the Phase 1b portion of
the study, a preliminary analysis of the data collected up to 6 months will be performed for
these patients.

Confidentiality Statement

- Once all patients enrolled in Combination Cohort 1, as well as the 2 patients enrolled into the
 open label portion of Combination Cohort 2, have completed the Day 180 follow-up visit,
 unblinding will be done and an interim analysis will be performed.

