5 DATA SETS TO BE ANALYZED

The following analysis sets will be used for the statistical analysis and presentation of data:

- **The Safety (SAF) Analysis Set.** The safety population will include all patients who received at least one dose of AG019. Only patients with clear documentation that no study medication was received may be excluded from analysis. Patients will be analyzed according to dose received. This population will be used for all data summaries.
- **The Pharmacodynamic Intention To Treat (PD-ITT) Analysis Set.** All patients in the repeat dose and combination cohorts who received at least one dose of AG019 will be included in the PD-ITT analysis set.
- **The Pharmacodynamic Per Protocol (PD-PP) Analysis Set.** All data from patients in the repeat dose and combination cohorts who received at least 75% of the scheduled doses of AG019* and at least one dose of teplizumab in the combination cohorts and had no major protocol deviations affecting the main PD endpoints at the time point of data collection** will be included in the PD-PP analysis set.

* XXXXXXXXXXXXXXXXXXXXXXX

** XXXXXXXXXXXXXXXXXXXXXXX

All patients to be included in the PD-ITT and PD-PP Analysis sets will be determined before data base lock. The Safety Set is considered the primary analysis dataset, and will be used for safety presentations and all other data summaries (except for PD summaries). All summaries will be performed according to dose received. Baseline presentations will be based on the safety set.

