6.3.3 Patient/Subject Data Listings

Data collected in the Case Report Forms (CRFs) will generally be listed in Appendix 16.2 (see section 7.2). CRF check questions [e.g. Lab samples taken (Yes/No)] and reminders will not always be listed.

Listings will be sorted by cohort, treatment group and patient number and parameter and visit/time point as applicable.

In CRF modules where a date is recorded, the date and the relative day will be included in the corresponding listing. In modules where both a start date and stop date are recorded, the duration will be given.

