6.3.8 Adverse Events

AEs will be coded according to the Medical Dictionary for Regulatory Activities (MedDRA) system.

The severity of adverse events will be given in grades 1 to 5 per National Cancer Institute common terminology criteria for adverse events (CTCAE) version 4.0.

All AEs were categorized by the Investigator with respect to their possible relationship to the IMP. The relationship of the AE to AG019, as well as the relationship of the AE to teplizumab, will be assessed separately by the investigator to be not related, unlikely, possible, probable or definite. The categorization:

- reasonably related defined as possible, probable or definite versus
- not reasonably related defined as not related or unlikely will be given in summaries of all adverse events.

If a subject has more than one event with the same preferred term (PT), then the worst severity and the worst relationship will be used.

A TEAE is defined as any adverse event (AE) not present prior to the initiation of the treatment(s) or any AE already present that worsens in either intensity or frequency following exposure to the treatment(s). Hence, events with an onset time at or after the time of treatment start are treatment emergent. Events present at baseline that worsen during the study in either intensity or frequency are also treatment emergent, whereas events present at baseline that become less severe during the study are not. Events that recur during the study are treatment emergent if they recur after complete or partial recovery of the initial event, i.e. should the event first become less severe and then return to its initial severity, it will be considered as a TEAE. AEs reported on the same day as treatment start or after treatment start will be considered TEAEs, as investigators are instructed only to report TEAEs after treatment start.

A Serious Adverse Event (SAE) is defined as any AE occurring at any dose regardless of relationship to IMP that results in any of the following outcomes:

- results in death,
- is life-threatening,
- requires inpatient hospitalisation or prolongation of existing hospitalisation,
- results in persistent or significant disability/incapacity, or
- is a congenital anomaly/birth defect.

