If the start date of an AE is missing, it will be assumed that the AE started after the first administration of IMP. If the start date of an AE is partially missing, and it has started the same year and/or month as the IMP it will be assumed that the AE started after the first administration of IMP. If an AE occurred on the same day as dosing but the onset time is missing the AE will be assumed to be a TEAE.

The infusion of teplizumab was considered withheld if the answer to the CRF question 'Was the Teplizumab infusion given?' was 'No, infusion not started' and/or if the answer on the AE page on 'Action Taken With Study Treatment Teplizumab' was 'Drug interrupted' or 'Drug withdrawn'.

Study treatment of AG019 was considered discontinued if the answer to the CRF question "Action Taken with Study Treatment AG019" was "Drug interrupted" or "Drug withdrawn".

A summary table per cohort will present number of TEAEs, number of unique TEAEs (counted once within each subject at the preferred term level) and number of subjects with at least one event for TEAEs, SAEs, related TEAEs, TEAEs leading to discontinuation of IMP/withdrawal and more.

Tables with

- All AEs by System Organ Class (SOC) and PT,
- All TEAEs by SOC and PT, in total and for the AG019 treatment period only,
- All TEAEs by SOC and PT according to severity, in total and for the AG019 treatment period only,
- All TEAEs by SOC and PT according to relatedness, in total and for the AG019 treatment period only,
- All serious TEAEs by SOC and PT,

will be given. If there are no events an empty table will be produced.

All AEs will be listed. In addition all TEAEs leading to AG019 treatment discontinuation and study infusion withholding will be listed.

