6.9 Interim Analysis

Preliminary results (interim analysis 1) for the open-label part of the study and a second interim analysis (described in the Interim Analysis Plan [IAP]) has been performed previously.

The primary analysis will be performed when all patients have passed the Day 180 visit. This interim analysis will contain the same TFLs that will be produced for the final output, if possible.

All decisions on data for blinded subjects will be taken before breaking the blind for the third interim analysis. Since this is a study of descriptive nature, with no statistical tests, the influence of the interim analyses should be considered negligible.

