16.2.2 Protocol Deviations

16.2.3.x Patients Excluded from the Pharmacodynamic Analysis
(Evaluable, Reason for Evaluable Classification)
Treatment Allocation and Evaluable for All Subjects

- 16.2.4.x Demographics and Other Background Characteristics
 - Medical History
 - History of T1D (diagnosis and insulin use)
 - Smoking, Alcohol and Illicit Drug Use
 - Inclusion Criteria Not Met and Exclusion Criteria Met
- 16.2.5.x Compliance to treatment with AG019
 - Compliance to treatment with teplizumab
- 16.2.6.x Pharmacodynamic Measurements:
 - HbA1c
 - Insulin dose adjusted HbA1c
- 16.2.7.x Adverse Events
 - Adverse Events for patients with infusion withholding
- 16.2.8.x Listing of Individual Laboratory Measurements
- 16.2.9.x Vital Signs
- 16.2.10.x Physical Examination
- 16.2.11.x ECG
- 16.2.12.x Concomitant Medication and Therapy (including insulin medication)
 - Prior Medications and Therapies
 - Concomitant Medications and Therapies []
- 16.2.13.x Hypoglycemic Events

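### No summary table listed in the SAP shows Phase 2a TEAEs for the randomised patients alone; adding one would be a cheap improvement

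*SAP*

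**What the plan says.** Protocol 3.1 describes Phase 2a as a randomised, double-blind part that compares AG019 plus teplizumab with placebo. Protocol 3.3, 5.2.2 and 5.9 and SAP 4.1.2 give the structure of each combination cohort: 12 patients, of whom the first 2 receive active treatment open label and the remaining 10 are randomised 4:1.

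SAP 6.3.2 then defines the groups for summary: "The groups will be divided into single dose for 2 and 6 capsules, repeat dose for 2 and 6 capsules, Active and Placebo". Its Table 1 gives each combination cohort two rows, one for AG019 with teplizumab and one for double placebo. SAP 5 adds: "All summaries will be performed according to dose received". Protocol 10.3.1 has the same rule for the safety population.

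The primary endpoint (SAP 3.1) is TEAE incidence up to the 6-month visit. SAP 7.1 lists an overall adverse event summary for the combination cohorts and TEAE tables by SOC and PT, severity, relationship to AG019, seriousness and AG019 discontinuation. Some are repeated for the AG019 treatment period. No title is limited to, or split by, randomised status.

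On causality, SAP 6.3.8 says: "The relationship of the AE to AG019, as well as the relationship of the AE to teplizumab, will be assessed separately by the investigator". For individual data, SAP 6.3.3 says: "Listings will be sorted by cohort, treatment group and patient number". SAP 7.2 includes a listing titled "Treatment Allocation and Evaluable for All Subjects".

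**The concern.** The primary-endpoint tables are the whole analysis of Phase 2a safety in this SAP, because no model or test is planned. A reader who sees an active and a placebo column from a part described as randomised and double blind will take them as a randomised, blinded comparison. As planned, they are not quite that.

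The open-label patients differ from the rest of the active row by design. They enter first, their data are reviewed in stages before others are treated, and they had no chance of placebo. Their events are reported, and causality judged, with treatment known. For randomised patients, Protocol 5.10 keeps the patient, the site and the sponsor (apart from the clinical supply manager) blinded for the first 6 months, the same window as the primary endpoint. The active column therefore mixes two conditions of reporting, while the placebo column has only one.

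**Working it through.** **Step 1. The plan's own total.** Four AG019 cohorts of up to 6 repeat dose patients and two combination cohorts of 12 give 4 × 6 + 2 × 12 = 48, the stated maximum (Protocol 4.1, SAP 4.1).

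**Step 2. Planned make-up of the rows** (Protocol 5.9, SAP 4.1.2).
- Randomised per cohort: 12 − 2 = 10.
- Randomised active: 10 × 4/5 = 8. Placebo: 10 × 1/5 = 2.
- Active row: 8 + 2 = 10, with an open-label share of 2/10 = 20%.
- Both cohorts together: 16 + 4 = 20 active and 4 placebo, with an open-label share of 4/20 = 20%.

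**Step 3. How far the displayed incidence can move.** Let k of the 8 randomised active patients and j of the 2 open-label patients have a TEAE. Then

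displayed − randomised-only = (k + j)/10 − k/8 = j/10 − k/40 = 0.2 × (j/2 − k/8).

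| k of 8 | j of 2 | Randomised active | Displayed active | Difference (points) |
|---|---|---|---|---|
| 8 | 0 | 100% | 80% | −20 |
| 4 | 0 | 50% | 40% | −10 |
| 4 | 1 | 50% | 50% | 0 |
| 4 | 2 | 50% | 60% | +10 |
| 0 | 2 | 0% | 20% | +20 |

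The event counts are illustrations. The documents give no event rates.

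**Step 4. Sensitivity to the planned 8 and 2.** No block size is given. Under simple 4:1 randomisation, exactly 8 of 10 active has probability 45 × 0.8⁸ × 0.2² = 0.30. With 7 or 9 randomised to active, the open-label share would be 2/9 = 22% or 2/11 = 18%. The size of the point barely changes.

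**Step 5. The placebo side.** With 2 patients, incidence can only be 0%, 50% or 100%, with or without the extra columns.

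**Step 6. Whether another planned output fills the gap.** Protocol 10.7 allows summaries to be repeated by study phase, but Phase 2a contains both kinds of patient. The listings show individuals and do not summarise the randomised groups, and their titles name no open-label/randomised flag.

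**Step 7. Timing.** SAP 6.9 reports that, after the open-label preliminary results, "a second interim analysis (described in the Interim Analysis Plan [IAP]) has been performed previously". In Protocol 10.8 the second analysis covers all of Combination Cohort 1 and the 2 open-label patients of Combination Cohort 2, at which point "unblinding will be done and an interim analysis will be performed". That is 12 + 2 = 14 patients, including 10 of the 20 randomised patients, if the analysis followed that schedule.

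**The case against.** The case for leaving the tables alone is a fair one. The SAP follows the protocol's dose-received rule. Open-label and randomised active patients have the same planned regimen. The study is descriptive (SAP 6.4, 6.5), so no test or estimate is invalidated. For detecting harms a row of 10 is better than one of 8: with no events, the one-sided 95% upper limit is 1 − 0.05^(1/10) = 25.9% against 1 − 0.05^(1/8) = 31.2%. Placebo stays at 2. The causality argument bears on the relatedness tables more than on TEAE incidence itself, and no passage shows that knowing the treatment changed reporting. With only 4 open-label patients planned, a reader may be able to separate them by hand from the listings.

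Most of this stands, and it limits the point to an improvement. It argues for keeping the all-active column, which the fix does. It does not supply a summary of the randomised groups for the primary endpoint.

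Three stronger readings are tempting and not supported:
- A reader might infer that the SAP states the merging outright, citing "A summary table per cohort will present number of TEAEs" or the absence of planned subgroups in SAP 6.8. Neither shows it: SAP 6.3.2 also splits by treatment group, and a statement on subgroups does not settle table columns. The merging is inferred from Table 1 and the dose-received rule.
- A reader might take 20 points as the bias. It is reached only if all 8 randomised active patients have an event and neither open-label patient does, or the reverse. The actual size and direction are unknown.
- A reader might call the layout an error. It contradicts nothing in the plan.

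**Conclusion.** The point holds as a cheap improvement, not as an error. Each planned Phase 2a active row is 20% open label, and the displayed TEAE incidence can differ from the randomised-active incidence by between −20 and +20 points, or by nothing if the two kinds of patient agree.

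This assumes exact 4:1 allocation in each cohort, no net change from replacement or drop-out, and Table 1 taken as the column layout. Table shells and the Interim Analysis Plan are not in the documents and might show the split. The point covers only the summary tables listed in this SAP; the PK, MMTT, immune-marker and mechanistic analyses lie outside it (SAP 1).

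**What to change.** In the Phase 2a TEAE tables, at least the overall summary and the SOC/PT table, keep the all-active column and add randomised-active and open-label-active columns beside placebo. Planned numbers per cohort are 8 randomised active, 2 open-label active and 2 placebo. A pooled randomised display of 16 against 4 is optional.

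Define membership by the IRT randomisation record. Enrolment order is not safe: Protocol 4.1 and 4.5 and SAP 4.2 allow replacement, and the documents do not say whether the substitute for an open-label patient is treated open label. Add an open-label/randomised flag to the treatment allocation listing.

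State in the SAP and the study report that the display was added after the first two interim analyses. The IRT record was set without reference to outcomes, so the split itself is not data-driven, but the timing should be visible.

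The cost is a SAP update and two more columns per combination cohort (from 2 to 4) in the affected tables. No protocol amendment is needed for this. The drawback is very small columns, with placebo groups of 2 that still say little.

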6.3.3 Patient/Subject Data Listings

Data collected in the Case Report Forms (CRFs) will generally be listed in Appendix 16.2 (see section 7.2). CRF check questions [e.g. Lab samples taken (Yes/No)] and reminders will not always be listed.

Listings will be sorted by cohort, treatment group and patient number and parameter and visit/time point as applicable.

In CRF modules where a date is recorded, the date and the relative day will be included in the corresponding listing. In modules where both a start date and stop date are recorded, the duration will be given.

6.3.4 Demographic and Other Baseline Characteristics

Demographic data and baseline characteristics will include:

- age
- sex
- ethnicity
- weight and body mass index (BMI)
- insulin use (%) and numbers of units per kilo body weight,
- baseline HbA1c, and insulin dose adjusted according to baseline HbA1c
- presence of Glutamic Acid Decarboxylase 65 (GAD65) antibodies, Insulinoma-Associated Protein 2 (IA-2) antibodies, zinc transporter 8 (ZnT8) antibodies and insulin antibodies
- Infectious diseases: Epstein-Barr Virus (EBV), Cytomegalovirus (CMV), human immunodeficiency viruses (HIV), Hepatitis B (HBV) and Hepatitis C (HCV)
- time from diagnosis to study treatment start
- time from insulin start to treatment start
- tobacco, alcohol and illicit drug consumption

Subject disposition, demographic data and other baseline data will be presented using summary statistics.

Some data as laboratory measurements, vital signs and physical examination are measured at baseline, but also at other visits. Baseline data for these parameters will be presented together with the rest of the data in by-visit displays. Physical examination included visual inspection of skin, examination of eyes, ears and throat, auscultation of heart, lungs and abdomen, and percussion/palpation of abdomen.

The medical history comprises a general medical history (including history of alcohol abuse, illicit drug abuse and smoking history), relevant T1D related medical history (including date of diabetes diagnosis, relevant glycaemia levels, autoantibody positivity, current insulin use and start date of insulin therapy as applicable) and medication history.

